14.6 Compliance Reference Documents

The Declaration of Helsinki, the consolidated ICH-GCP, and other applicable law(s) and guidelines in the country where the trial takes place shall constitute the main reference guidelines for ethical and regulatory conduct.

15 LIABILITIES AND INSURANCE

15.1 ICH-GCP Responsibilities

The responsibilities of Ferring, the monitor, and the Investigator are defined in the ICH-GCP consolidated guideline and applicable regulatory requirements in the country where the trial takes place. The Investigator is responsible for adhering to the ICH-GCP responsibilities of Investigators, for dispensing the IMP in accordance with the approved protocol or an approved amendment, and for its secure storage and safe handling throughout the trial.

15.2 Liabilities and Insurance

Ferring is, as Sponsor, responsible for ensuring appropriate general/product liability insurance and, as required in accordance with applicable laws and regulations, country-specific liability insurance coverage for claims made by a trial subject for injury arising from the subject's participation in the trial.

16 ARCHIVING

16.1 Investigator File

The Investigator is responsible for maintaining all the records, which enable the conduct of the trial at the site to be fully understood, in compliance with ICH-GCP. The trial documentation, including all the relevant correspondence, should be kept by the Investigator for at least 15 years after regulatory approval, if no further instructions are given by Ferring.

The Investigator is responsible for the completion and maintenance of the confidential subject identification code, which provides the sole link between identifiable subject source records and de-identified data in the clinical database for Ferring. The Investigator must arrange for the retention of this Subject Identification Log and signed Informed Consent Documents for at least 15 years after regulatory approval.

No trial site document may be destroyed without prior written agreement between the Investigator and Ferring. Should the Investigator elect to assign the trial documents to another party, or move them to another location, Ferring must be notified. If the Investigator retires and the documents can no longer be archived by the site, Ferring can arrange having the Investigator File archived at an external archive.

16.2 Trial Master File

Ferring will archive the Trial Master File in accordance with ICH-GCP and applicable regulatory requirements.

Appendix B Dietary Guidelines for Diabetics

Additional Guidelines for Diabetes Management

Even though you will be on a diet of clear fluids for the whole day before your colonoscopy examination, it is still possible for you to get sufficient carbohydrates in this diet. Besides drinking lots of fluids, you must remember that these fluids need to contain sufficient amounts of carbohydrate. If you don't drink enough fluids, your blood sugars may go low, or surprisingly, they may begin to go higher.

Guidelines

- Follow your doctor's directions for taking your insulin or pills.
- Your blood sugars should be monitored regularly. Please discuss this with your doctor, nurse or dietician.
- You must meet your needs for more fluids. Drink a lot of water, clear soup, clear broth, sugar-free drinks, sugar-free popsicles, and sugar-free Jell-O. Your goal is to drink at least one tall glass of fluid every hour, and have plenty of fluids as your meals for the day. There is no restriction to these.
- In addition to fluids, you must also meet your needs for carbohydrate every hour. See the list below for the drink ideas and portion sizes for your hourly need during the day.

To get enough carbohydrate during the day, take one choice from this list every waking hour:

One quarter cup grape juice	One third cup apple juice
One third cup cranberry juice	One third cup pineapple juice
One half cup orange juice	One half cup grapefruit juice
One half cup regular pop or soda	One quarter cup regular Jell-O
One third cup regular Kool-Aid	One half popsicle
One quarter cup sherbet	Two hard candies

Call the doctor

[figure not shown]
- If you have persistent nausea or vomiting.
- If you have questions or worries.

Appendix C Modified Aronchick Scale and Boston Bowel Preparation Scale

Modified Aronchick Scale (Aronchick et al, 1999, as cited by ASGE, 2015)¹

Grade	Description
Excellent	>90% of mucosa seen, mostly liquid stool, minimal suctioning needed for adequate visualization
Good	>90% of mucosa seen, mostly liquid stool, significant suctioning needed for adequate visualization
Fair	>90% of mucosa seen, mixture of liquid and semisolid stool, could be suctioned and/or washed
Inadequate	<90% of mucosa seen, mixture of semisolid and solid stool which could not be suctioned or washed

Boston Bowel Preparation Scale²

- 0 Unprepared colon segment with mucosa not seen due to solid stool that cannot be cleared.
- 1 Portion of mucosa of the colon segment seen, but other areas of the colon segment not well seen due to staining, residual stool, and/or opaque liquid.
- 2 Minor amount of residual staining, small fragments of stool and/or opaque liquid, but mucosa of colon segment seen well.
- 3 Entire mucosa of colon segment seen well with no residual staining, small fragments of stool or opaque liquid.

Appendix D Mayo Clinic Bowel Prep Tolerability Questionnaire

MAYO CLINIC BOWEL PREP

TOLERABILITY QUESTIONNAIRE

PROTOCOL 000253 – FERRING PHARMACEUTICALS

SITE No.: _____ PI NAME: _____

SUBJECT No.: _____ S _____

Please follow these instructions:

- Complete this questionnaire **PRIOR** to colonoscopy procedure
- Mark the most appropriate response according to your current experience with the bowel preparation (for example ✓)
- Return this questionnaire to the Study Coordinator. If the SC is not available, place the questionnaire in a sealed envelope and provide it to a member of the surgical team

Date: _____

1. How many bowel movements did you have in the week prior to starting colon preparation?
 - 3 or less/week
 - 4 to 8/ week
 - 9 or more a week
2. How much of the bowel preparation solution was left in the bottle after drinking it to your best effort?
 - Less than 25%
 - 25%-50% left
 - 50%-75% left
 - 75% or more left
3. How tolerable did you find the bowel preparation?
 - Easy
 - Acceptable
 - Somewhat difficult
 - Very difficult
 - Unacceptable
4. Based on your current experience, would you be willing to drink the same preparation again if you need another colonoscopy in the future?
 - Not willing at all
 - Somewhat willing
 - Mostly willing
5. In case you have experienced some difficulties in tolerating the bowel preparation, do you think that was due to your current health issues? (Check more than 1 option if applicable)
 - Yes
 - No
 - It does not apply to me (I did not have any difficulties tolerating bowel preparation)
 - It does not apply to me (I do not have any health issues)

The Mayo Clinic Bowel Prep Tolerability Questionnaire created by and used with permission from Mayo Foundation for Medical Education and Research © 2016. The permission granted herein will expire five years from 12Dec2016.

SITE No.: _____ PI NAME: _____ SUBJECT No.: _____

6. How much the following symptoms bothered you during bowel preparation?

Symptoms	None	Mild	Moderate	Severe
Bad taste in your mouth	1	2	3	4
Gastric fullness	1	2	3	4
Lack of sleep from excessive bathroom trips	1	2	3	4
Nausea/vomiting	1	2	3	4
Bloating/abdominal distention/gas	1	2	3	4
Abdominal pain/cramps	1	2	3	4
Headache	1	2	3	4

Others (please specify the symptom (s) and indicate how bothersome it was):

7. Is this your first colonoscopy procedure?

- No (please, answer the following questions)
 Yes (end of the questionnaire)

8. Which type of bowel preparation did you take in your previous colonoscopy?

- GoLyteLy (1 gallon tasteless/salty solution)
 Moviprep (1/2 gallon flavored solution)
 MiraLax (Over the counter colon preparation)
 Other (please specify): _____
 Don't remember

9. In comparison with your previous experience, how would you rate your tolerability of the current bowel preparation?

- Worse than before
 About the same as before
 Better than before

Thank you very much for completing this questionnaire.

Disclaimer:

Mayo Foundation for Medical Education and Research (MFMER) grants you a limited, revocable, worldwide, English-only right to use the Mayo Clinic Bowel Prep Tolerability Questionnaire for non-commercial academic research. In addition, MFMER will allow for one-time only translation of the Mayo Clinic Bowel Prep Tolerability Questionnaire into the following languages: Spanish, French Canadian and Russian.

The Mayo Clinic Bowel Prep Tolerability Questionnaire is provided as-is with no warranties or guarantees as to its fitness for a particular purpose. MFMER is not responsible for providing updates of any kind but any updates provided will be governed under the permission described herein.

The Mayo Clinic Bowel Prep Tolerability Questionnaire created by and used with permission from Mayo Foundation for Medical Education and Research © 2016. The permission granted herein will expire five years from 12Dec2016.

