- Proportion of subjects classified as a responder defined by a score ≥ 2 in the right segment of the colon using the Boston Bowel Preparation Scale (BBPS)² ([Appendix C](#))
- Proportion of subjects classified as a responder defined by a score ≥ 2 in the transverse segment of the colon using the BBPS² ([Appendix C](#))
- Proportion of subjects classified as a responder defined by a score ≥ 2 in the left segment of the colon using the BBPS² ([Appendix C](#))
- Frequency of each category of the Mayo Clinic Bowel Prep Tolerability Questionnaire³ ([Appendix D](#))
- Incidence of treatment-emergent AEs and clinically significant changes in vital signs, ECGs, and laboratory values
- Plasma concentration of sodium picosulfate, magnesium and active metabolite bis-(p-hydroxyphenyl)-pyridyl-2-methane (BHPM)

METHODOLOGY

The study will be conducted at approximately 10-15 study sites in the US and Canada.

Following appropriate informed consent procedures, subjects who fulfill eligibility criteria and require a colonoscopy will be randomized to one of two treatment arms.

Only the subject and the site-designated unblinded coordinator and or pharmacist (if applicable) will know the treatment group in which the subject will be participating. The designated unblinded coordinator will instruct the subject on the use of the bowel preparation, and both will sign a nondisclosure affidavit form, attesting to their agreement that they will not disclose the treatment group to anyone. Treatment will be blinded to the designated endoscopist and study site personnel assessing the efficacy of the two tested preparations.

Following randomization, subjects will perform colon cleansing using NaP/MC Oral Solution or PREPOPIK[®] as follows:

For each treatment arm, subjects will begin treatment (first dose) the evening before colonoscopy between 5:00 and 9:00 PM, and will complete treatment (second dose) the following day, at least 5 hours, but no more than 9 hours, prior to the colonoscopy.

NaP/MC Oral Solution (supplied as two 160-mL bottles per subject) needs no further reconstitution before administration.

After drinking the first dose, subjects should drink five (5) or more eight-ounce glasses of clear liquid within five (5) hours.

After drinking the second dose, subjects should drink four (4) or more eight-ounce glasses of clear liquid within five (5) hours. Subjects should not take anything by mouth within two (2) hours before the time of the colonoscopy.

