5.1.1 Investigational Medicinal Product (IMP)

Sodium Picosulfate, Magnesium Oxide and Anhydrous Citric Acid (NaP/MC) Oral Solution

Dose: Sodium Picosulfate, Magnesium Oxide and Anhydrous Citric Acid (NaP/MC) Oral Solution will be provided as two 160-mL bottles to be administered in divided doses.

The first dose is administered the evening before the colonoscopy between 5:00 PM and 9:00 PM. The second dose is administered at least five (5) hours, but no more than nine (9) hours, prior to the colonoscopy.

Preparation: NaP/MC Oral Solution is supplied as two 160-mL bottles per subject and needs no further reconstitution before administration.

Compliance will be documented in the eCRF. Subjects will be considered compliant if the dosing occurs within 30 minutes of specified timings above.

After drinking the first dose, subjects should drink five (5) or more eight-ounce glasses of clear liquid within five (5) hours. After drinking the second dose, subjects should drink four (4) or more eight-ounce glasses of clear liquid within five (5) hours. Subjects should not take anything by mouth within two (2) hours before the time of the colonoscopy.

PREPOPIK[®]

Dose: PREPOPIK[®]: Is supplied as two (2) packets per subject. One dose is prepared by combining the contents of one packet with approximately five (5) ounces of water.

Subjects will take the first dose the evening before the colonoscopy between 5:00 and 9:00 PM and will complete the treatment (second dose) the following day at least 5 hours prior but no later than 9 hours prior to the colonoscopy.

Preparation: Mix the contents of one (1) packet with cold water (approximately five (5) ounces) in the cup provided. Stir for two to three minutes and drink the solution. In some cases the cup may feel warm, which is normal.

Compliance will be documented in the eCRF. Subjects will be considered compliant if the dosing occurs within 30 minutes of specified timings above.

After drinking the first dose, subjects should drink approximately five (5) eight-ounce glasses of clear liquid within five (5) hours. After drinking the second dose, subjects should drink three (3) eight-ounce glasses of clear liquid within five (5) hours. Subjects should stop taking anything by mouth two (2) hours before the time of the colonoscopy.

Note: Liquids with **red, purple, or blue coloring are not allowed** before the colonoscopy.

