5.2.1.2 PREPOPIK[®]

PREPOPIK[®] is a white crystalline powder for oral solution and will be supplied in two (2) packets. Each packet of PREPOPIK[®] contains the following ingredients:

- Sodium Picosulfate 10.0 mg
- Magnesium Oxide, Light 3.5 g
- Citric Acid, Anhydrous 12.0 g

Magnesium oxide and anhydrous citric acid react in solution to form magnesium citrate.

PREPOPIK[®] is manufactured and supplied by Ferring Pharmaceuticals for the U.S. market in boxes containing two packets and a dosing cup.

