6.2 Randomization Visit (Visit 2)

Randomization Visit 2 (V2) takes place ≤ 10 days from the Procedure/Colonoscopy Visit. For **females of childbearing potential**, the Randomization Visit (V2) **must occur within three (3) days prior to the colonoscopy** procedure. Females of childbearing potential **must** have a **negative urine pregnancy test** result at randomization. For males and postmenopausal women, the Randomization Visit (V2) must occur ≤ 10 days prior to the colonoscopy procedure (see Section 6.3). The following will be performed:

If the study screening requirements are met:

- Confirm eligibility
- Measure orthostatic vital signs (blood pressure and pulse)
- Measure body weight

- Urine pregnancy test (onsite) for females of childbearing potential (For females of childbearing potential randomization **must occur within three (3) days** prior to the colonoscopy procedure. Females of childbearing potential **must** have **a negative urine pregnancy test** result at randomization within 3 days prior to the colonoscopy.)
- Assign Subject Randomization number
- Dispense study medication
- Instruct the subject how to self-administer the study medication and provide them with a Subject Diary Card and detailed information, complete with assigned times of drug administration
- Provide the Acceptability and tolerability questionnaire to be completed prior to the procedure Visit (V3)
- Adverse events (recorded by study personnel)
- Document any new concomitant medications

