6.3 Procedure/Colonoscopy Visit (Visit 3)

If the subject is participating in the PK subset, additional laboratory samples will be obtained for sodium picosulfate and BHPM at the following timepoints:

- 15 minutes before the second dose of IMP
- 1 to 2 hours after the second dose of IMP
- 3 to 6 hours after the second dose of IMP

Immediately prior to the colonoscopy, a PK sample will be obtained for **all participating subjects** in the study (approximately 2 hours prior to the colonoscopy).

Before the colonoscopy, the following will be performed:

- Treatment completed
- Collect Subject Diary Card
- Collect the Acceptability and tolerability completed questionnaire*
- Obtain orthostatic vital signs (blood pressure and pulse)
- Measure body weight
- Obtain laboratory sample (chemistry, hematology)
- Adverse events (recorded by study personnel)
- Document any concomitant medications

- PK subset only: PK samples for sodium picosulfate and BHPM 15 minutes before the second dose, and 1 to 2 hours and 3 to 6 hours after the second dose of the IMP
- All subjects: PK sample immediately prior to colonoscopy (approximately 2 hours prior to the colonoscopy)
- Perform study drug accountability by the unblinded coordinator or unblinded pharmacist (if applicable)

*Subjects should be instructed to fill out the questionnaire during the visit in a private area prior to contact with the Investigator and to return the completed questionnaire to the study coordinator. If the coordinator is not available during the procedure, the subject will put the completed questionnaire in a sealed envelope and provide it to a member of the surgical team. The study coordinator should check each questionnaire for completion, and if the subject did not answer all/some of the questions, note the reasons on the first page of the questionnaire. No one (including study coordinator or a family member) should interpret questions or response choices for the subject.

During the colonoscopy procedure, the blinded endoscopist will:

- Video-record the colonoscopy
- Use the Modified Aronchick Scale (see [Appendix C](#)) to score the quality of the bowel preparation in the overall colon after use of the study drug
- Use the Boston Bowel Preparation Scale (see [Appendix C](#)) to score the quality of the preparation in the different segments of the colon after use of the study drug
- Record the outcome of the colonoscopy

After the colonoscopy procedure, the following will be performed/recorded:

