9.6.3.4 Tolerability and Satisfaction

Mayo Clinic Bowel Prep Tolerability Questionnaire (see [Appendix D](#)) questions 2, 3, 4, 6 (for each category), and 9 will be analyzed separately and summary statistics will be provided for all individual questions by randomized treatment group for the mITT population. The Wilcoxon Rank Sum 2-sided test will be used for the treatment comparison of ordered categorical variables.

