### **8.1.2 Treatment Compliance**

The number and proportion of subjects deviating from the treatment regimen will be summarized by treatment group for the safety population. The summary will include the following:

- the number of patient that did not consume the entire dose,
- deviations from protocol mandated administration time,
- the number of patients that did not fast two hours before colonoscopy,
- the number of patient that did not adhere to clear liquid diet 24 hours prior to colonoscopy and
- the number of subject that did not consume the recommended number eight-ounce glasses of clear liquid after each dose of IMP.

Furthermore, associated listing will be produced.

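### Mayo question 2 asks what was left in the bottle, but PREPOPIK has no bottle, so a between-arm difference on this item may partly reflect packaging and should not carry a formal test

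*Protocol*

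**What the plan says.** **The item.** One form serves both arms. Question 2 reads "How much of the bowel preparation solution was left in the bottle after drinking it to your best effort" (Protocol Appendix D; SAP Appendix 4 has the same words). The four answers run from under a quarter left to three quarters or more left. The two middle answers share the value of exactly one half.

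**The supplies.** The Protocol synopsis says "NaP/MC Oral Solution (supplied as two 160-mL bottles per subject) needs no further reconstitution before administration". For PREPOPIK, Protocol 5.1.1 says "Mix the contents of one (1) packet with cold water (approximately five (5) ounces) in the cup provided", and 5.2.1.2 describes supply "in boxes containing two packets and a dosing cup". Neither document mentions a bottle for PREPOPIK.

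**Help for the subject.** Protocol 6.3 bars everyone, including the coordinator, from explaining questions or answers. Neither document has a note on question 2 for the PREPOPIK arm.

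**The analysis.** Protocol 9.6.3.4 lists question 2 among the items to be analysed and adds: "The Wilcoxon Rank Sum 2-sided test will be used for the treatment comparison of ordered categorical variables". SAP 9.3.4 analyses every question, with the same test for ordered responses, and SAP 9.1 sets a two-sided 5% level. The endpoint itself (Protocol 2.2, SAP 2.2) is the frequency of each category.

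**Other intake data.** SAP 8.1.1 counts by arm the subjects who took each dose. SAP 8.1.2 summarises "the number of patient that did not consume the entire dose". Protocol 9.7 summarises the amount reported as consumed.

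**Timing of the form.** Protocol 6.2 (Visit 2) says "Provide the Acceptability and tolerability questionnaire to be completed prior to the procedure Visit (V3"). Protocol 6.3 says "Subjects should be instructed to fill out the questionnaire during the visit in a private area prior to contact with the Investigator". Protocol 7.1.3 and Table 1 also place it at Visit 3.

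**The concern.** The item names a container that only one arm has. A NaP/MC subject can look at a bottle. A PREPOPIK subject must decide what the word stands for: the cup, the last mixed dose, or the whole treatment. Staff may not help.

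The skipped second dose shows the problem best. On NaP/MC an unopened bottle of solution remains, so about half the treatment is visibly left. On PREPOPIK the second packet was never mixed, so no solution is left over and the lowest category is a literal answer. Two subjects who behaved identically could land in different categories because of how the product is packed. In addition, half left fits two of the printed answers.

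At stake is an item-level p-value within a named secondary endpoint. A packaging effect could be read as a difference in tolerability or intake.

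The timing line in Protocol 6.2 is a separate defect. A form completed before Visit 3 could be completed before dose 2, and questions 2, 3 and 6 would then miss that dose.

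**Working it through.** **Plan figures.** Neither document gives an expected distribution for question 2 or a rate of skipping dose 2, so there is no planned figure to reproduce. The only input taken from the plan is 450 subjects per arm. That number was set for the primary endpoint and does not depend on this item.

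**1. Does the wording alone create a bias?** Take a subject who takes dose 1 and skips dose 2.

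| Reading of the item | NaP/MC answer | PREPOPIK answer |
|---|---|---|
| Container just drunk from | under a quarter | under a quarter |
| Whole treatment | about half | about half |
| Solution physically left over | about half | under a quarter |

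Only the third row separates the arms. The same split would arise if the arms took different readings. The documents do not say which reading subjects will use.

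For a partly drunk dose, reading bottle as cup makes the two arms comparable: 160 mL per bottle against about 5 × 29.57 = 148 mL of water per packet.

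**2. Extreme-case illustration.** Assumptions: the same number k in each arm skips dose 2; all k NaP/MC skippers report about half left (one category); all k PREPOPIK skippers report the lowest category; everyone else reports the lowest category. With a and b subjects in the higher category and 450 per arm, the tie-corrected Wilcoxon statistic reduces to

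z² = 899(a − b)² / [(a + b)(900 − a − b)].

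| a vs b | Share skipping | z² | Wilcoxon p | Fisher p |
|---|---|---|---|---|
| 5 vs 0 | 1.1% | 899×25/(5×895) = 5.02 | 0.025 | 0.062 |
| 9 vs 0 | 2.0% | 899×81/(9×891) = 9.08 | 0.0026 | 0.0038 |
| 13 vs 0 | 2.9% | 899×169/(13×887) = 13.18 | 0.0003 | 0.0002 |

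At 5 vs 0 the data are too sparse to rely on the asymptotic p-value.

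**3. Relaxing the assumption.** Suppose about half of the PREPOPIK skippers also report half left.

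| a vs b | z² | Wilcoxon p |
|---|---|---|
| 5 vs 2 | 899×9/(7×893) = 1.29 | 0.26 |
| 9 vs 4 | 899×25/(13×887) = 1.95 | 0.16 |
| 13 vs 6 | 899×49/(19×881) = 2.63 | 0.10 |

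These typical counts are not significant, but the error rate is still raised. Let the counts be binomial, with skip rate s on NaP/MC and a reported rate s/2 on PREPOPIK. Summing the probability of all pairs with z² > 3.84 gives about 12%, 22% and 33% false rejection at s = 1%, 2% and 3%. With equal reporting in both arms the same sum gives 4% to 5%.

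**4. Other ways of misreading.** These were simulated with 450 per arm, identical true intake, 90% to 98% of both arms truly in the lowest category, the two-sided 5% Wilcoxon test, and 1,000 runs per setting.

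| PREPOPIK subjects' behaviour | False rejection |
|---|---|
| Read bottle as cup | 4% to 5% |
| 2% wrongly pick a higher category | 13% to 41% |
| 5% wrongly pick a higher category | 54% to 96% |
| 10% default to the lowest category | 6% to 8% |
| 50% default to the lowest category | 22% to 80% |
| 2% to 50% leave it blank at random | 4% to 6% |

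The direction also changes: wrongly picking a higher category makes PREPOPIK look worse, and defaulting to the lowest makes it look better.

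**5. Timing.** Protocol 6.2 has the form completed before Visit 3. Protocol 6.3, 7.1.3 and Table 1 have it completed at Visit 3, and 6.3 lists treatment completion first among the pre-procedure steps. Dose 2 is taken on the day of colonoscopy, so only the 6.2 line allows completion before it.

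**The case against.** A reader might infer that the test compares two different quantities and is biased in a known direction, hiding missed PREPOPIK doses. The documents do not support that. The item speaks of one bottle and of what was drunk. Read that way, a NaP/MC subject who emptied the first bottle and never opened the second may also give the lowest answer. Read as the whole treatment, a PREPOPIK subject with an unused packet may report half. Either reading, applied to both arms, gives equal answers. This objection stands, and it is why no size or direction is claimed.

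It can also be said that intake is measured elsewhere, that the endpoint is a frequency table, and that the item lies outside the gated sequence of primary non-inferiority, right-colon non-inferiority and superiority. All true. This limits the consequence, but it also means that little is lost by dropping the test.

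The overlapping answer categories affect both arms and belong to an instrument that the protocol calls validated and uses under its owner's permission. That stands too, and no change to the form is asked for.

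On timing, Protocol 3.6.2 and 10.3 and the SAP copy of the form also point to the day of colonoscopy, so the 6.2 line looks like a stray. It affects both arms equally and is not a source of between-arm bias.

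What survives is that the wording fits one arm only, nobody may clarify it, and a formal between-arm test is planned on it.

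**Conclusion.** The point holds in a limited form. Question 2 does not fit the PREPOPIK arm, no instruction bridges the gap, and a between-arm difference on it may partly reflect packaging. The bias could be nil or substantial depending on how subjects read the item, and the documents do not allow it to be estimated. The p-values for k against 0 are an extreme case that rests on an assumed skip rate and on opposite readings in the two arms.

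The primary and right-colon conclusions, the sample size and the type I error control are unaffected. The conflict between Protocol 6.2 and the other sections is real, separate and editorial. Both defects are worth correcting because the correction is cheap. Neither threatens the trial's main result.

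**What to change.** 1. In SAP 9.3.4 and Protocol 9.6.3.4, report question 2 as category frequencies by arm, without the Wilcoxon test, and note that its wording does not fit PREPOPIK. Compare intake with data already planned: number taking each dose (SAP 8.1.1), number not finishing the entire dose (SAP 8.1.2) and amount consumed (Protocol 9.7). These use the safety set, whereas the questionnaire uses the mITT set, so the table notes should say so.

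2. Reconcile Protocol 6.2 with 6.3, 7.1.3 and Table 1, so that the form is completed only after dose 2 and before the procedure. If forms are already in hand, their date line would show any completed before the day of colonoscopy.

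**Cost.** One questionnaire item loses its p-value, and a few lines of text change. No new data are needed. The form stays as it is; rewording question 2 would be an alternative, but may need the owner's agreement.
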